5.2 Eligibility

The following are inclusion and exclusion criteria that determine facility and child eligibility:

Facility inclusion:

- ξ Consenting government-designated healthcare facilities within the selected geographical areas of each country
- ξ Providing curative primary care services for children 0 – 59 months of age
- ξ Oxygen available or referral mechanism in place with oxygen available at a higher level facility
- ξ Electricity available (from any source with continuous or intermittent supply)

Facility exclusion:

- ξ Attending to fewer than 20 sick children per month (based on the prior 12 month average)
- ξ Already using pulse oximetry as a routine part of outpatient-based consultations of children 0 – 59 months
- ξ Selected to be part of a major child health programmatic or research intervention during the study period likely to significantly affect the primary outcome
- ξ Inaccessible to the study team (e.g. due to weather conditions or security issues) for significant parts of the year.

Individual child inclusion:

- ξ Children 0 – 59 months for whom caregivers provide consent
- ξ Consulting for an illness, or reported to be unwell when attending for a routine visit (e.g. vaccination, growth or chronic disease monitoring)

Individual child exclusion:

- ξ Children in the immediate post-natal period or first day of life
- ξ Attending for a consultation related to trauma only (including new and follow-up presentations for burns, injuries, wounds)
- ξ Admitted within an inpatient part of the facility (including neonates delivered at the facility admitted with their mother)
- ξ Enrolled in the study within the preceding 28 days at any study facility

5.3 Recruitment

The number of participants enrolled will be presented in a flowchart for pre and post intervention, together with the number of potential participants not recruited due to the child's eligibility failure, caregiver's refusal to consent or caregiver being underage. Reasons for eligibility failure will be summarised.

Further enrolment figures will be presented by facility type, location and district and a graph will be produced showing monthly and cumulative recruitment.

Additionally, the percentage of eligible children (no. eligible/no. screened) and the percentage of recruited children (no. recruited/no. eligible) will be provided, overall and pre and post intervention.

5.4 Withdrawal/Follow-up

The number of children for which follow-up at Day 7 was conducted will be presented in a flowchart for pre and post intervention. Reasons for withdrawals will be provided if available.

5.5 Baseline Participant Characteristics

Socio-demographic data of children enrolled and their caregivers will be summarised. Additional characteristics of interest, such as danger signs and symptoms as reported by the caregiver, will be presented as part of baseline summaries. Baseline data will be presented separately pre and post intervention using median and associated interquartile range (IQR) if continuous and as counts and percentages if categorical. Summary statistics will be of non-missing values, with the number (%) of missing values given if data are not complete. Assessment will be made for baseline changes between two time periods by visual inspection only and no formal testing will be performed.

For the baseline summaries, age of children will be reported as a continuous variable in months but also disaggregated in age groups. In the database, the age is estimated based on recommended standardised age disaggregation groups [2] with a different level of accuracy depending on the information provided by the caregiver. Based on age estimates, children are further categorised into young infants (<60 days) and children 60days-59 months. More details are provided in Appendix A.

6 ANALYSIS

Analyses will be performed and reported overall and by country.

Outcomes will be presented separately for young infants (<60 days) and older children (60 days-59 months), the malaria-related outcomes will be presented only on older children.

6.1 Outcomes Definitions

This section presents general definitions, applicable to multiple outcomes, and a detailed definition of each primary and secondary outcome.

Outcomes definitions are grouped by topic rather than primary and secondary outcomes.

6.1.1 General definitions

Day 7 assessment

Day 7 assessment refers to information reported by the caregiver after Day 0 and recorded in Day 7 form. Data collected as part of unscheduled visits are also integrated in these forms. If multiple successful follow-up assessments for the same child are recorded within the Day7 database, the most recent follow-up assessment will be used. To limit potential recall bias, assessments conducted far beyond the expected follow-up time will be dropped, i.e. 30 days from Day 0.

Death

A child will be considered deceased if, from Day 7 assessment, his/her status at the time of follow-up is “deceased”. In case of implausible death date (i.e. prior to enrolment date), death will be assumed to be within 7 days of Day0.

Hospitalisation

A child will be considered hospitalised if, from Day 7 assessment, he/she went to a hospital, was admitted overnight or if his/her status at the time of follow-up is “hospitalised”. In case of implausible hospitalisation date (i.e. prior to enrolment date), hospitalisation will be assumed to be within 7 days but after 24hrs of Day0.

Hospitalisation within 24hrs of Day0

For the purpose of primary analysis, a child will be considered admitted to hospital within 24hrs of Day0 consultation if the date of hospitalisation is the same as Day0 date or is one day after Day0 date.

Referral

A child will be considered to be referred (either to a hospital or to an inpatient part of a larger primary healthcare facility) if, at Day0, the research assistant confirms that an urgent referral advice was recorded for the child. If urgency is unknown, referral will be assumed to be urgent.

Antibiotics

Antibiotics will be defined in accordance with the WHO antibiotic point prevalence survey (PPS) methodology [4, 5, 6] and therefore only antibacterials for systemic use will be taken into account.

SpO2 values

SpO₂ should be recorded during the Day0. For the outcomes, the following measures will be taken for spurious and missing SpO₂ values:

- If SpO₂ value is not available, the child will be assumed normoxaemic
- If $70 \leq \text{SpO}_2 < 90\%$, the child will be assumed (with accuracy) to have severe hypoxaemia
- If $40 \leq \text{SpO}_2 < 70\%$, the child will be assumed (with low accuracy) to have severe hypoxaemia
- If $\text{SpO}_2 < 40\%$, the value will be considered spurious (e.g. due to incorrect dataentry) and treated as not available, i.e. the child will be assumed normoxaemic.

Additionally, a description of SpO₂ values distribution will be provided based on the following cut-offs:

- $95\% \leq \text{SpO}_2 < 100\%$
- $94\% \leq \text{SpO}_2 < 95\%$
- $92\% \leq \text{SpO}_2 < 94\%$
- $90\% \leq \text{SpO}_2 < 92\%$
- $70\% \leq \text{SpO}_2 < 90\%$ (severe hypoxaemia, accuracy)
- $40\% \leq \text{SpO}_2 < 70\%$ (severe hypoxaemia, but low accuracy)
- Spurious ($0\% \leq \text{SpO}_2 < 40\%$)
- Missing

Mild hypoxaemia

$92\% \leq \text{SpO}_2 < 94\%$ (Kenya)

Moderate hypoxaemia

$90\% \leq \text{SpO}_2 < 92\%$ (Kenya)

$92\% \leq \text{SpO}_2 < 95\%$ (Senegal)

Severe hypoxaemia

$\text{SpO}_2 < 90\%$ (Kenya)

$\text{SpO}_2 < 92\%$ (Senegal)

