6.1.2 Health, hospitalisation and referral outcomes

6.1.2.1 Proportion of children with a severe complication by Day 7

Severe complication is defined as death or secondary hospitalisation. Secondary hospitalisation refers to any delayed hospitalisation (occurring at any point greater than 24hrs after the Day 0 consultation) and any hospitalisation occurring without a referral. Information on death and hospitalisation will be taken from Day7 follow-up assessment.

Death will be counted in the numerator if death date is within 7 days of Day0 (7th day included). Hospitalisation will be counted in the numerator if the child was not referred at Day0 or hospital admission date is within 7 days of Day0 (7th day included) but after 24hrs of Day0.

The denominator will be all children recruited. Children for whom no death and hospitalisation data are available or withdrew prematurely from the study will be assumed to be alive and not hospitalised by Day7.

6.1.2.2 Proportion of children admitted to hospital within 24 hours of Day 0 consultation and as a result of a referral

Information on hospitalisation will be taken from Day7 follow-up assessment.

Hospitalisation will be counted in the numerator only if the child received a referral advice (as per definition above) at Day0 and hospital admission date is within the end of the following day. The denominator will be all children recruited.

Additionally, the proportion will be calculated and reported using only children who were referred as denominator.

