6.3 Missing Data

Missing values will be primarily due to children lost to follow-up and not reached at Day 7.

Primary outcomes are based on information collected at Day0 through a structured data collection process that prevents missing values due to compulsory data entry. Therefore, missing data on the primary outcomes are not anticipated.

Analysis on secondary outcomes that rely on Day 7 follow-up data will be performed assuming the best case scenario (alive and not hospitalised) for children lost to follow-up or withdrawn.

Additionally, missing data will be described by pre and post intervention period and by relevant indicators, such as referral and severe disease to visually inspect for imbalances.

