6.5 Harms

Safety of the interventions will be evaluated in terms of deaths and secondary hospitalisations that occurred throughout the course of the study. Deaths, secondary hospitalisations and both combined will be reported as counts and percentages. Summary statistics will be presented separately for each intervention as outlined in Section 4.3.

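### A death by Day 7 that is learned only from a contact more than 30 days after Day 0 is discarded, and the child is analysed as a survivor

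*SAP*

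**What the plan says.** Five rules in the SAP act together.

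- **Late assessments (6.1.1).** "To limit potential recall bias, assessments conducted far beyond the expected follow-up time will be dropped, i.e. 30 days from Day 0". If a child has several successful assessments, the most recent is used. The order of these two steps is not stated, nor is whether Day 30 itself is kept.
- **Definition of death (6.1.1).** "A child will be considered deceased if, from Day 7 assessment, his/her status at the time of follow-up is" recorded as deceased.
- **Source and window (6.1.2.1).** "Information on death and hospitalisation will be taken from Day7 follow-up assessment". A death counts by its own date, up to and including the 7th day, not by the date of the call.
- **No data.** Section 6.1.2.1: "Children for whom no death and hospitalisation data are available or withdrew prematurely from the study will be assumed to be alive and not hospitalised", with all recruited children in the denominator. Section 6.3 repeats this for outcomes that need Day 7 data: "performed assuming the best case scenario (alive and not hospitalised) for children lost to follow-up or withdrawn". Section 6.1.2.7 assumes that children without Day 7 data are cured.
- **Harms (6.5).** "Safety of the interventions will be evaluated in terms of deaths and secondary hospitalisations that occurred throughout the course of the study".

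The Protocol (7.1.1) schedules the call for Day 7 to Day 10.

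**The concern.** The stated reason for the cut-off is recall bias. That is a good reason to discard a late account of recovery, care-seeking or the timing of an admission. It is a weak reason to discard the fact that a child died. The cut-off does not leave such a child's outcome unknown. Combined with the best-case assumption, it replaces a reported death with survival.

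Severe complication is the first-listed secondary outcome, and deaths are one of the two components of the safety evaluation. Both are likely to be rare, so a handful of reclassified deaths could matter.

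**Working it through.** **1. Following a death on Day 4 through the rules**

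| Contacts | Late assessments dropped first | Most recent chosen first, then dropped |
|---|---|---|
| Only a Day 35 call, reporting the death | No data: alive, not hospitalised, cured | No data: alive, not hospitalised, cured |
| Alive at a Day 3 visit integrated in the Day 7 form, then a Day 35 call reporting the death | Death not counted | No data: alive, not hospitalised, cured |
| Death reported on Day 8 and again on Day 35 | Death counted | No data: alive, not hospitalised, cured |
| Only a Day 29 call, reporting the death | Death counted | Death counted |

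The same death on the same date counts if first reported on Day 29 and becomes survival if first reported on Day 35. The third row shows that the unstated order can lose even a death reported on time.

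**2. What the cut-off adds for other outcomes**

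Completed referral (6.1.2.5), cure (6.1.2.7) and the caregiver-reported visits (6.1.6) already require a follow-up date no later than Day 10 for the numerator. Severe complication has no such limit. For numerators, then, the 30-day rule works mainly on deaths and hospitalisations.

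**3. Whether anything restores these deaths**

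Protocol 7.2.4 extends the search of referral-level records to children lost to follow-up, but the SAP does not use those records to define death. None of the sensitivity analyses in SAP 6.2.4 restores late assessments or varies the best-case assumption.

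**4. Size**

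The plan gives no figure for late calls, loss to follow-up or mortality, so there is none to reproduce. For scale, take the initially planned numbers per period in Protocol 6.6.1. These can be reproduced: 3% against 4.5% at 80% power and two-sided alpha 0.05 needs 2,518 children per period before clustering.

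- Kenya: design effect 1 + (690 − 1) × 0.005 = 4.445; 2,518 × 4.445 = 11,193; 17 facilities × 690 = 11,730.
- Senegal: design effect 1 + (510 − 1) × 0.005 = 3.545; 2,518 × 3.545 = 8,926; 18 facilities × 510 = 9,180.

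Let *p* be mortality by Day 7 and *f* the share of those deaths known only from a contact after Day 30. Both are assumptions: *p* from 0.1% to 0.5%, *f* from 5% to 30%.

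Deaths lost per period = N × *p* × *f*:

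- Kenya: 11,730 × 0.001 × 0.05 = 0.6, up to 11,730 × 0.005 × 0.30 = 17.6.
- Senegal: 9,180 × 0.001 × 0.05 = 0.5, up to 9,180 × 0.005 × 0.30 = 13.8.

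The observed post/pre ratio of deaths is the true ratio × (1 − *f* post) / (1 − *f* pre):

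- Equal *f*: factor 1. The ratio is unchanged and only the level is too low in each period. A risk difference in death shrinks by the factor 1 − *f*.
- 5% pre and 20% post: 0.80 / 0.95 = 0.84.
- 20% pre and 5% post: 0.95 / 0.80 = 1.19.

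These figures are for deaths alone. Severe complication also counts secondary hospitalisations, so the proportional change in that composite is smaller. The documents give no figure from which to say by how much.

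**The case against.** The strongest reply is that contacts after Day 30 are off-schedule and may be very few, and that nothing in the documents shows late contact to be commoner after a death or different between periods. That stands, and it limits what can be said about size.

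A second reply is that a common cut-off gives both periods the same limit of ascertainment, whereas keeping late deaths makes the count depend on how long calling went on. This has some force, and it is why dropped assessments should be counted by period. But keeping late deaths creates no new asymmetry between the dead and the living: a survivor reached late is already taken as alive, so only the deaths are misclassified now.

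A third is that the date of death is itself subject to recall. True, but 6.1.1 keeps a death dated before enrolment and assumes that it fell within 7 days. That rule addresses a different problem, but it shows that the SAP does not otherwise discard a death because its date is poor.

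A reader might also infer two stronger points that the documents do not support. One is that 6.1.1 contradicts 6.5. Section 6.5 says which events are summarised and 6.1.1 says which assessments are usable; 6.5 states no assumption of survival, so at most it inherits the under-count. The other is that late-reported admissions should be kept as well. Admission dates separate primary from secondary hospitalisation, so there the recall argument applies.

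**Conclusion.** The point holds as a rule that misclassifies a known outcome. It needs two conditions: the death fell within 7 days of Day 0, and no usable assessment by Day 30 reported it. Such a child is then analysed as a survivor for severe complication, including the breakdown by SpO₂ group in 6.1.5.2. With no other data the child is also counted as cured. The death would be absent from the harms counts if the 6.1.1 definition governs 6.5.

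Both primary outcomes are measured at Day 0 and are untouched. The number of cases cannot be derived from the documents and may be small; the ranges above rest wholly on assumed mortality and an assumed share of late reports. It would go too far to read the rule as a demonstrated bias in the pre/post comparison: a distorted ratio of deaths requires late reporting to differ between periods, and the SAP specifies no separate model for death. The change is still worth making before analysis, because it is cheap and the current rule turns reported deaths into survivors.

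**What to change.** In SAP 6.1.1:

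1. Keep vital status and date of death from any contact, whenever made, and classify the death by its date against the Day 7 limit. A child with a retained death by Day 7 should not be assumed alive or cured.
2. Apply the 30-day drop to all other caregiver-reported items, including hospital admissions, and say whether Day 30 itself is kept.
3. State that the drop is applied before the most recent assessment is selected.
4. Report the number of dropped assessments by period and by reported status (alive, hospitalised, deceased). This will show whether the issue is trivial.

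The cost is a few sentences, a small change to the derivation code and one short table. The downside is that a few death dates taken from late calls will be less exact.

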Data that will be collected at Day 7 follow-up will include cure status (recovery from illness as reported by the caregiver), hospitalisation and death between Day 0 and Day 7. If appropriate, name of the referral facility and duration of hospitalization will be collected to facilitate the retrospective data collection at referral hospital level.

Higher level of care visit

Data collection at this level of care will be conducted retrospectively. A quantitative research assistant using the EDC mobile application will collect data from referral facility records, registries and discharge summaries for children whose caregiver reported at Day 7 phone follow-up that they attended a government-designated referral facility between Day 0 and Day 7. This includes attendance to hospital or emergency / inpatient area of a larger primary or secondary care facility (e.g., study facilities that can admit paediatric patients). Personally identifiable information will be collected to cross-check the identity of the patients. Arrival date and time, basic clinical information on arrival and, if admitted, admission and discharge diagnosis and admission duration will be collected. If available, data on oxygen saturation at admission, oxygen administration and intensive care unit (ICU) admission and duration will also be recorded.

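### The SAP's rule for hospital dates before enrolment counts a referred child admitted promptly, but with a date slip, as a severe complication: a small, cheaply fixed misclassification in secondary and harms outcomes

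*SAP*

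**What the plan says.** SAP 6.1.1 (Hospitalisation) gives one rule for hospital dates that fall before enrolment, with no condition on referral: "hospitalisation will be assumed to be within 7 days but after 24hrs of Day0". The same section counts an admission as within 24 hours "if the date of hospitalisation is the same as Day0 date or is one day after Day0 date".

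Two secondary outcomes use that date:

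- **Severe complication (SAP 6.1.2.1).** A hospitalisation counts under either of two conditions: "the child was not referred at Day0 or hospital admission date is within 7 days of Day0 (7th day included) but after 24hrs of Day0".
- **Admission within 24 hours as a result of referral (SAP 6.1.2.2), the proxy for appropriate referral.** The child must have been referred, with this limit on timing: "hospital admission date is within the end of the following day". The stated source is the caregiver: "Information on hospitalisation will be taken from Day7 follow-up assessment".

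SAP 6.5 also tabulates secondary hospitalisations as a harm.

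A second source exists. Protocol 7.1.1 (Higher level of care visit) has research assistants search the records of government-designated referral facilities: "Arrival date and time, basic clinical information on arrival and, if admitted, admission and discharge diagnosis and admission duration will be collected". Protocol Tab. 4 lists the visit and admission form as TIMCI-04b. The SAP takes oxygen use from hospital records (6.1.5.4) but does not use those records to resolve an impossible admission date.

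**The concern.** The rule decides which outcome class a referred child falls into, and it always picks the unfavourable one. Only urgent referrals, or referrals of unknown urgency, count as referrals in SAP 6.1.1. For an urgently referred child who is admitted, a date just before enrolment could well be a slip for Day 0 or Day 1. The SAP gives no reason for assuming a late admission.

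One slip of this kind makes two errors: it adds a child to an adverse outcome and takes the same child out of a favourable one. The number of children exposed grows with the number referred and admitted, which the intervention is meant to raise. A slip rate that is equal in both periods therefore adds somewhat more false complications after the intervention than before, and they also appear in the harms table.

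**Working it through.** **1. What the rule does.** The definitions in SAP 6.1.1, 6.1.2.1 and 6.1.2.2, applied to a hospitalised child:

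| Referred at Day 0 | Recorded admission day | Severe complication | Within 24 h after referral |
|---|---|---|---|
| Yes | 0 or 1 | No | Yes |
| Yes | 2 to 7 | Yes | No |
| Yes | before 0 (rule applies) | **Yes** | **No** |
| No | any | Yes | No |

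The third row differs from the first in both columns. The last row does not depend on the date. So for these two outcomes the rule matters only in referred children.

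**2. Inputs.**

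- From the documents: pre-intervention referral 3% (Protocol 6.6.1, SAP 3.4). Protocol 6.6.1 expects that a 50% rise in referral may bring only a 20-30% rise in completed referrals.
- Assumed, because the documents give no figure: 40-60% of referred children admitted by Day 1 pre-intervention; 2-5% of those dates recorded before enrolment, equal in both periods; true severe-complication rate 0.5-1% in both periods; admissions rising in line with completed referrals.

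**3. False complications per 10,000 children.** Pre = referral rate × admitted share × slip rate × 10,000. Post = pre × 1.2 to 1.3.

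- Pre, low: 0.03 × 0.40 × 0.02 × 10,000 = 2.4. Pre, high: 0.03 × 0.60 × 0.05 × 10,000 = 9.0.
- Post, low: 2.4 × 1.2 = 2.9. Post, high: 9.0 × 1.3 = 11.7.

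**4. As counts.** The initial sample sizes in Protocol 6.6.1 reproduce: 3% versus 4.5% at two-sided 5% and 80% power needs 2,518 per period. The Kenya design effect is 1 + 689 × 0.005 = 4.445, giving 11,193, or 17 facilities × 690 = 11,730. The Senegal design effect is 3.545, giving 8,926, or 18 × 510 = 9,180. They serve here only for scale. The rule then creates about 2.8-10.6 false complications pre and 3.4-13.7 post in Kenya, and 2.2-8.3 pre and 2.6-10.7 post in Senegal.

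**5. False odds ratio for severe complication, with no true effect.** OR = odds(true rate + post false rate) / odds(true rate + pre false rate).

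- Low end, true rate 1%: odds(0.010288) / odds(0.010240) = 1.005.
- High end, true rate 0.5%: odds(0.006170) / odds(0.005900) = 1.046.
- With a slip rate of 0.5%, false complications are 0.6-0.9 per 10,000 pre and 0.7-1.2 post, and the OR is 1.001-1.005.

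**6. Against sampling error.** Ignoring clustering, the 95% interval for the OR with 11,730 per period extends by a factor of exp(1.96 × √(2 / (11,730 × p × (1 − p)))) either way. This is 1.29 at p = 1% and 1.44 at p = 0.5%. Clustering would widen it.

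**7. Within-24-hours outcome.** If a share s of true early admissions is lost in each period, both proportions are multiplied by (1 − s), so their ratio does not change. The absolute level falls by 2-5% of itself under these assumptions.

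**8. Do the planned sensitivity analyses cover it?** SAP 6.2.4 varies the cut-off between primary and secondary hospitalisation (same day, 3 days, 7 days).

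- Same day: the child stays a complication. That is wrong if the true admission was on Day 0.
- 3 days: the class is undefined, because the rule supplies no exact day.
- 7 days: the child becomes a primary hospitalisation and leaves complications. But so does every referred child truly admitted on Days 2 to 7, so this does not isolate the date rule.

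**The case against.** The case for leaving the rule alone has five parts.

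- **Such dates may be rare.** Protocol 7.2.2 describes range and consistency checks at entry and daily quality checks, and 7.2.4 adds repeat-call audits. None names the hospital date, and the SAP still plans for such dates, but a slip rate below 2% is quite possible. This stands, and it makes the size uncertain at the low end.
- **The rule is conservative.** It leans against the intervention and does not hide harms. That is true of its direction, but the SAP does not offer it as the reason, and it is not conservative elsewhere: SAP 6.3 assumes that children lost to follow-up are alive and not hospitalised.
- **Day 0 or Day 1 is not proven.** An early date could be a genuine earlier admission or a wrong month for a later one. This stands. A reader might infer that these admissions should simply be set to within 24 hours in the main analysis. The documents do not support that default any better than the present one.
- **The second source is incomplete.** A reader might infer that a recorded arrival date exists for every affected child. It does not: retrieval covers government-designated facilities in the study area and needs an identity match (Protocol 7.1.1, 7.2.4), while private admissions are known only from the caregiver. Arrival is also not quite admission.
- **A 7-day cut-off analysis is already planned.** It gives part of the alternative classification, with the limit shown in step 8.

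**Conclusion.** The misclassification follows directly from the SAP's definitions. Its likely size is small: under the stated assumptions, 2.4-9.0 false complications per 10,000 pre and 2.9-11.7 post, and a false odds ratio of about 1.005-1.05, well inside the sampling error. With slips at 0.5% or fewer it is negligible.

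Three stronger readings are tempting and should be resisted.

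- A reader might infer 50% more false complications post than pre, from the 3% to 4.5% referral assumption. That needs an unchanged admitted share among referred children. Protocol 6.6.1 expects completed referrals to rise by only 20-30%, and a child must complete referral to be admitted because of it.
- A reader might infer that the pre-post comparison of the within-24-hours outcome is distorted. With equal slip rates both periods lose the same proportion, so the relative effect is nearly unchanged.
- A reader might infer a threat to the main conclusions. Referral and antibiotic prescription are Day 0 outcomes and do not use the hospital date.

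What remains is a minor, avoidable error in a secondary outcome and the harms table, which no planned analysis tests directly.

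**What to change.** Amend the rule in SAP 6.1.1:

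1. Where the caregiver's hospital date precedes Day 0, use the referral-facility arrival date (form TIMCI-04b) if a matched record exists.
2. For referred children whose date is still unresolved, report 6.1.2.1 and 6.1.2.2 with the admission treated as within 24 hours and as after 24 hours, without presuming that either is correct. Carry both into the secondary-hospitalisation rows of the harms table (6.5).
3. Report the number of pre-enrolment dates, resolved and unresolved, by period and referral status.

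The cost is some record linkage, a short SAP amendment and one extra sensitivity analysis. No new data are needed. If slips prove rare, the count in item 3 will show that the issue does not matter.
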